6.13.7.1 Analysis

The 5-level ordinal variable will be analysed using an ordinal logistic regression model. The model will include treatment as a fixed effect and baseline MELD score as a covariate.

Assumptions about the proportionality of odds will also be assessed. Should assumptions not hold, then the treatment odds ratios for the individual cumulative levels of the variable will be presented..

The adjusted LS estimate for the treatment odds and treatment odds ratio (DS102:Placebo) along with corresponding 95% CI and p-value (corresponding to the treatment odds ratio) will be presented.

6.13.7.2 Descriptive summaries and listing

The 5-level ordinal variable be listed and summarised by treatment group and visit.

6.14 Multiplicity

All secondary endpoints and the supportive analyses will be considered as descriptive evidence of efficacy and will be analysed without any procedures to account for multiple comparisons.

6.15 Pharmacokinetics

Pharmacokinetics analyses for the pilot and double-blind phases of the study will be conducted as detailed in Appendix 1 Pharmacokinetic Data Analysis Plan (PKAP). Only outputs relating to the double-blind phase will be produced as part of this SAP. Note the double-blind phase is referred to as treatment phase in the PKAP.

6.16 Safety Evaluation

6.16.1 Adverse Events

Adverse events (AEs) will be coded using the latest MedDRA dictionary version. The version used will be indicated in the data summaries and listings.

A treatment-emergent adverse event (TEAE) is defined as an AE that started on or after the start of the administration study treatment. If adverse event dates are incomplete and it is not clear whether the adverse event was treatment-emergent, it will be assumed to be treatment-emergent.

Any AE commencing after the last administration of study treatment may be considered treatment emergent.

A summary table by treatment and overall will present the following:

- TEAEs (events and patients).
- Serious TEAEs (events and patients).
- Serious study treatment related TEAEs (events and patients).
- TEAEs by pattern (intermittent/continuous/single event) (events and patients).
- TEAEs by severity (mild/moderate/severe) (events and patients).
- TEAEs by relationship to study treatment (events and patients).
- TEAEs leading to withdrawal from study (patients only).
- TEAEs leading to discontinuation of study treatment (patients only).
- Study treatment related TEAEs leading to discontinuation of study treatment (patients only).
- TEAEs leading to death (patients only).

In the above summaries, if a patient experienced more than one TEAE, the patient will be counted once using the most related event for the “by relationship to study treatment” and “related to study treatment” summaries and at the worst severity for the “by severity” summary. If a patient experienced more than one TEAE, the patient will be counted once for each pattern recorded. For summaries at the patient level, the number and percent of patients will be presented.

The above summary table will be presented for the pilot and double-blind phases.

The following tables will be presented:

- TEAEs by System Organ Class (SOC) and Preferred Term (PT).
- TEAEs by PT.
- TEAEs by SOC, PT and severity.
- TEAEs by SOC, PT and relationship to study treatment (related/ not related).
- Serious TEAEs by SOC and PT
- TEAEs leading to withdrawal by SOC and PT

For all of the above, SOC and PT will be presented in decreasing frequency of the total number of patients with TEAEs. Number of events and number and percentage of patients will be presented.

Further details of the above four tables are given below:

1. If a patient experienced more than one TEAE the patient will be counted once for each SOC and once for each PT.
2. If a patient experienced more than one TEAE, the patient will be counted once for each PT.
3. If a patient experienced more than one TEAE, the patient will be counted once for each SOC and once for each PT at the worst severity.
4. If a patient experienced more than one TEAE, the patient will be counted once for each SOC and once for each PT using the most related event.

Adverse event data will be listed in full and this will also include a treatment emergent flag, the time of onset and cessation of event percentage to first dosing of study treatment and duration of AE.

6.17 Clinical Laboratory Evaluation

Observed values and change from baseline in haematology, biochemistry, urinalysis, and coagulation assessments will be summarised over time. If the test results are reported in categorical format, the results will be summarised by patient counts and percentage for each category. Percentage change will be included on the biochemistry summary table.

Ratio of AST to ALT will be derived and presented along with the other assessments.

Each haematology, biochemistry, urinalysis and coagulation parameter will be classed as low, normal, high, missing based on the reference ranges. Shift tables in relation to the normal range from baseline over time will be presented.

Haematology, biochemistry, urinalysis and coagulation data will be listed separately including change from baseline, reference ranges flagging all out of range values and their clinical significance.

Listings of clinically significant haematology, biochemistry, urinalysis and coagulation laboratory measurements recorded throughout the study will be provided.

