## 11.3 Drug Induced Liver Injury (DILI)

### 11.3.1 Severe drug-induced liver injury

Irrespective of perceived causation, in the event of severe drug-induced liver injury (DILI) then the investigational drug should be discontinued until the episode is deemed to have resolved. In the event the investigational drug is deemed to be the cause of the liver injury then the patient should not be re-challenged with the drug.

Potential severe DILI in the study population (severe acute decompensated AH patients with impaired baseline liver biochemistry) stipulates evidence of hepatic impairment as demonstrated by:

- Total bilirubin >2x baseline and ALT and/or AST >3x baseline (confirmed by immediate repeat testing)
- Total bilirubin >3x baseline (confirmed by immediate repeat testing)
- ALT and/or AST >5x baseline (confirmed by immediate repeat testing)
- ALT and/or AST >500 U/L (confirmed by immediate repeat testing)
- Alkaline Phosphatase  $\geq$ 5x baseline
- An increase in MELD score > 10
- Lille score > 0.85

Prompt (within 24 hours) adjudication of events of possible DILI or treatment failure, as listed above, will be performed by an independent expert in AH and DILI with recommendations for or against drug discontinuation.

Other causal factors should be considered and if found they must be discussed with the sponsor before investigational product is restarted.

Even if patients discontinue the investigational drug they should still be encouraged to attend study visits for continued study data collection.

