### 11.3.2 Monitoring of patients with impaired liver biochemistry

Abnormalities of liver biochemistry indicating evidence of hepatic impairment as listed above should be followed by repeat testing within 48-72 hours to confirm/determine if the biochemical changes are improving or worsening. AE information should be collected alongside a thorough physical examination. A liver aetiology screen and/or other appropriate testing should be undertaken. In the event of liver dysfunction then the patient should be managed as a severe drug-induced liver injury (see above). Pausing of drug treatment should be considered if any of the criteria in the previous section occur.

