## 12.7 Safety Analysis

Demographic information, medical history and physical examination data will be listed for each patient and summarised descriptively.

All AEs recorded during the study will be coded to system organ class and preferred terms using the current version of the Medical Dictionary for Regulatory Activities (MedDRA). Treatment-

emergent AEs will be tabulated and summarised by treatment, relationship to treatment, seriousness and severity. Non-treatment emergent AEs will be listed separately.

Clinical laboratory values (haematology, biochemistry, and coagulation) will be listed for each patient by treatment and day. Values outside the laboratory normal ranges will be listed separately with associated comments as to their clinical significance, with potentially clinically significant abnormalities highlighted and summarised by treatment. Clinical laboratory values obtained prior to dosing will be defined as baseline values.

Individual values of vital signs will be listed and summarised descriptively for each treatment and day.

ECG assessments will be listed for each patient with all associated comments and summarised by treatment and day.

Concomitant medications (if any), categorised by medication group and subgroup according to the latest version of the World Health Organisation drug dictionary (WHODD), will be listed and summarised by treatment.

In general, appropriate descriptive statistics, according to the nature of the variable, will be applied. Categorical variables will be presented using counts and percentage, whilst continuous variables will be presented using mean, standard deviation, median, minimum, maximum, coefficient of variation and number of patients.

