6.5 Data presentations

The data will be summarised in tabular form by treatment group apart from disposition of patients, protocol deviations, 'background and demographic' data and adverse events which will be summarised by treatment group and overall patients. Treatment labels will be "1000 mg DS102 (BD)", "Placebo (BD)" and "All Patients" (where applicable).

Only scheduled post-baseline laboratory, electrocardiogram (ECG), nutritional status assessment, cytokeratin18-M30/M65 and vital signs values will be tabulated, post-baseline repeat/unscheduled assessments will be disregarded, although they will be listed and in particular all clinically significant values will be noted (where applicable).

Analysis sets will be summarised using the enrolled set. Study completion/withdrawal and protocol deviations will be summarised using the RAN set. Background and demographic characteristics will be summarised using the FAS. The primary efficacy endpoint will be summarised using the FAS and the PPS. Secondary endpoints will be based on the FAS only. Prior/concomitant medications, administration of study treatment and exposure and safety will be summarised using the SAF. PK (double-blind phase) will be summarised using the PK (double-blind phase) set.

PK (pilot phase) will be based on the PK (pilot phase) set, PK (double-blind phase) will be based on the PK (double-blind phase), safety listings will be based on the SAF set, and all other listings will be based on the enrolled set.

Listings will be sorted by phase, treatment group, patient number and date/time of assessment.

Treatment groups will be presented in the following order “Pilot phase: 1000 mg DS102 (BD)”, “Double-blind phase: 1000 mg DS102 (BD)” and “Placebo (BD)”.

Graphical presentations of the data will also be provided where appropriate.

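### No by-arm laboratory table counts patients meeting the protocol's potential-DILI criteria, and the planned normal-range shift tables cannot show bilirubin worsening

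*SAP*

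**What the plan says.** **Laboratory tables.** SAP 6.17 sets the only laboratory categories: "Each haematology, biochemistry, urinalysis and coagulation parameter will be classed as low, normal, high, missing based on the reference ranges". It adds: "Shift tables in relation to the normal range from baseline over time will be presented". Continuous results get observed values and change from baseline, and "Percentage change will be included on the biochemistry summary table". For clinically significant results there is a listing: "Listings of clinically significant haematology, biochemistry, urinalysis and coagulation laboratory measurements recorded throughout the study will be provided".

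**Repeat tests.** SAP 6.5 tabulates only scheduled post-baseline laboratory values: "post-baseline repeat/unscheduled assessments will be disregarded, although they will be listed".

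**Liver criteria.** Protocol 11.3.1 gives seven indicators of potential severe DILI:
- bilirubin >2x with ALT and/or AST >3x baseline
- bilirubin >3x baseline
- ALT and/or AST >5x baseline
- ALT and/or AST >500 U/L
- ALP at least 5x baseline
- MELD rise >10
- Lille >0.85

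The first four carry a retest requirement, for example "Total bilirubin >3x baseline (confirmed by immediate repeat testing". Possible events go to an independent expert for adjudication. Under Protocol 11.3.2, such abnormalities "should be followed by repeat testing within 48-72 hours to confirm/determine if the biochemical changes are improving or worsening".

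**Protocol safety analysis.** Protocol 12.7 says values outside the normal range will be listed, "with potentially clinically significant abnormalities highlighted and summarised by treatment". SAP 6.25 declares four changes from the protocol; this is not one of them.

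**The concern.** The safety objective is a comparison of DS102 with placebo. Because these patients start with impaired liver biochemistry, the protocol measures liver injury mainly against each patient's own baseline. The SAP measures laboratory results against the normal range and does not mention DILI. For bilirubin, where entry forces an abnormal value, that category carries no information about worsening.

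The SAP already has a suitable method. For vital signs, SAP 6.18 counts patients whose blood pressure or heart rate changes from baseline by more than set amounts, at each time and at any post-baseline time point. The liver tests get no equivalent.

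At stake is whether the report can say how many patients in each arm met a potential-DILI criterion, and how many were confirmed. As planned, someone would have to assemble that from listings after unblinding, with the rules chosen at that point.

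**Working it through.** The plan gives no figure on this point to reproduce. The check uses the entry limits (Protocol 7.2 and 7.3), the criteria (Protocol 11.3.1), the visit schedule (Protocol Appendix 2), the summary statistics (SAP 6.1) and 60 patients per arm (SAP 3). Neither document gives laboratory reference ranges, so upper limits of normal (ULN) are assumptions.

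1. **Bilirubin.** Entry requires at least 5 mg/dl. For any ULN below 5, every eligible patient is High at baseline. From 5 mg/dl, >2x means >10 and >3x means >15. A rise to 16 is 16/5 = 3.2x and stays High to High, as does no change. The only visible movement is improvement.

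2. **AST.** Entry requires >50 U/L. If the ULN is 50 or less, all start High. From 51 U/L, >3x means >153 and >5x means >255, again High to High. With a ULN above 50, some patients could start normal.

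3. **ALT, ALP, gamma GT.** ALT has no lower entry limit. The AST:ALT ratio must exceed 1.5, so AST just above 50 forces ALT below about 50/1.5 = 33.3 U/L, while AST of 400 allows ALT up to 400/1.5 = 266.7. For an assumed ALT ULN of 35, 40, 45 or 50, patients with AST below 1.5 x ULN = 52.5, 60, 67.5 or 75 must have normal ALT. ALP and gamma GT have no entry limit. Normal-to-high shifts are possible for all three.

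4. **Repeat tests.** An immediate repeat is unscheduled. A 48-72 hour retest is 2 to 3 days later. Scheduled days are 0, 3, 5, 7, 14, 21, 28 and 90. Day 5 or Day 7 could serve as the retest of a value seen two days before. From Day 7 to Day 28 nominal visits are 7 days apart, so a retest falls between them unless visit windows happen to meet. It then appears only in listings.

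5. **Continuous summaries.** These give n, mean, SD, minimum, quartiles, median and maximum, with percentage change for biochemistry.
   - The patient going from 5 to 16 has (16 - 5)/5 = +220%. If seen at a scheduled visit, that arm's maximum percentage change is at least +220%.
   - The maximum does not say how many patients exceed +200% (that is, 3x). If the maximum is above +200% and the upper quartile is not, the count among 60 patients could be anything from 1 to 60 x 0.25 = 15.
   - The joint bilirubin-and-transaminase criterion cannot be recovered from separate summaries.
   - Illustration with assumed numbers: 3 of 60 patients rising by 11 mg/dl move the arm mean by 3 x 11/60 = 0.55 mg/dl.

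6. **What a count would deliver** (assumed true rates). The chance of at least one case among 60 is 1 - (1 - p)^60: 0.45, 0.70 and 0.95 for p = 1%, 2% and 5%. Fisher's exact test with 60 per arm has power 0.33 for 5% v 15% and 0.85 for 5% v 25%. The table would be descriptive.

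**The case against.** A reader might infer that a liver signal cannot appear in any by-arm categorical table. The documents do not support that. SAP 6.16.1 plans by-arm tables of treatment-emergent events by class, term, severity and relationship, of serious events, and of events leading to withdrawal, discontinuation or death. SAP 6.12.10 counts 2-point m-SOFA worsening, and level 3 of the ordinal variable in SAP 6.13.7 covers early termination for safety or lack of efficacy. ALT and ALP shifts can show worsening, and the laboratory maxima expose an extreme scheduled value.

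Three other strong readings also fail:
- Not every liver test is abnormal at entry; the entry limits settle this only for bilirubin and, under the assumption above, AST.
- Repeat tests are not lost. They are listed, and unscheduled pre-dose values can define baseline (SAP 6.3). The rule in SAP 6.5 does not name MELD or Lille.
- The protocol does not name liver injury as this drug's specific risk. Its risk assessment describes good tolerability, and section 11.3 concerns management of individual patients, including possible treatment failure. It promises no table.

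What remains is that none of these outputs is a count of patients meeting the criteria. The adverse event route depends on an event being reported. Relatedness is a weak filter here, because Protocol 11.1.3 classes an event as not related if another cause can explain it, and the underlying disease often could. Level 3 mixes safety with lack of efficacy.

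**Conclusion.** The point holds in limited form. No by-arm laboratory table counts patients meeting any of the seven Protocol 11.3.1 criteria. The bilirubin shift table cannot show worsening, assuming only a ULN below 5 mg/dl; the same is true of AST if its ULN is 50 U/L or less. Post-baseline confirmatory values, where unscheduled, sit in listings only. The by-treatment summary in Protocol 12.7 has been reduced to a listing, and SAP 6.25 does not declare it.

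This is a gap in how safety is presented. It does not hide all liver toxicity: a signal could reach the adverse event tables if reported, or the laboratory maxima. It should be corrected before unblinding, while the counting rules can still be set without knowledge of treatment.

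**What to change.** In SAP 6.17, keep the existing shift tables and add:
- One descriptive by-arm table on the safety analysis set, with the number and percentage of patients meeting each Protocol 11.3.1 criterion, and any criterion, at any post-baseline time, using scheduled and unscheduled values.
- In that table, the number confirmed for the four criteria with a retest requirement and, where captured, the adjudicated outcome. Protocol 11.3.1 and 11.3.2 give different retest timings, and these passages must be reconciled before confirmation can be programmed.
- Maximum post-baseline multiple of baseline for bilirubin and AST, by arm.

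Exempt these worst-value tables from the SAP 6.5 rule. Restore the Protocol 12.7 by-treatment summary, or declare its removal in SAP 6.25.

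The cost is SAP wording and a few tables, with no new visits or samples. There are two drawbacks. Retested patients contribute more values and so have more chances to cross a threshold; show the number of values per patient by arm. Raw counts also mix disease progression with drug injury, so they should be labelled descriptive and read beside any adjudicated outcomes.

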6.18 Vital Signs

Vital sign observed values and change from baseline by parameter (unit) will be summarised over time.

In addition, 'substantial' changes from baseline will be categorised as follows: change from baseline in systolic/diastolic blood pressure (systolic BP [<-40 mmHg, $>+40$ mmHg], diastolic BP [<-20 mmHg, $>+20$ mmHg]) and heart rate [<-30 bpm, $>+30$ bpm]). The number and percentage of patients with changes from baseline as categorised above will be summarised separately for positive and negative changes over time and at any post-baseline time point.

All vital sign data will be listed including change from baseline and flags for substantial changes from baseline, reference ranges flagging all out of range values and their clinical significance.

A listing of clinically significant vital signs recorded throughout the study will be provided.

6.19 Electrocardiography

The overall interpretation of the ECG (Normal, Abnormal Not Clinically Significant (NCS), and Abnormal Clinically Significant (CS)) will be summarised over time.

All ECG data will be listed.

6.20 Physical Examination

Details of timings of physical examinations will be listed.

6.21 Pregnancy test

Pregnancy test details will be listed.

6.22 Exploratory Blood Collection

Exploratory blood collection data will be listed.

6.23 Liver Histopathology

Liver Biopsy History and Liver histopathology data including Non-Alcoholic Steatohepatitis (NASH) activity grading and fibrosis staging will be summarised and listed.

6.24 Nutritional Status Assessment

Bedside subjective global assessment will be scored as (0,1,2 and 3). Patients will be classified into the following categories: well nourished (0), mild malnutrition (1), moderate malnutrition (2) and severe malnutrition (3).

BMI will be recorded on the eCRF.

Nutritional status assessment data will be summarised and listed.

6.25 Changes from the Protocol Planned Analysis

The study protocol refers to a total population set however no analyses will be performed using this set because screen failures will not be databased.

The study protocol section 5.3 states that exploratory endpoints for APACHE-II and Lille scores will be change from baseline to Day 7, 14 and 28, this SAP is also including change from baseline to Day 21 as an exploratory outcome to be in-line with other outcome measures.

The study protocol section 5.4 states that SUSARs will be one of the safety endpoints, reporting of these is not covered by this SAP.

The study protocol section 12.9.1 refers to calculation and reporting of PK parameters for the double-blind phase. These will not be carried out as part of the PKAP and will not be reported as part of this SAP.

Syne qua non study no: ANE18001

Afimmune study no: DS102A-05-AH1

CV%	Percent coefficient of variation
D	Dose
DAP	Data analysis plan
dp	Number of decimal points
DSMB	Data safety monitoring board
Flucp	Fluctuation at pharmacokinetic steady-state
GeoMean	Geometric mean
K_{el}	Apparent first-order terminal elimination rate constant
LC/MS-MS	Liquid chromatography tandem mass spectrometry
PC	CDISC-compliant concentration dataset
PK	Pharmacokinetic(s)
PP	CDISC-compliant pharmacokinetic dataset
R_{ac}	Accumulation ratio at pharmacokinetic steady-state
SD	Standard deviation
SOP	Standard operating procedure
$t_{1/2}$	Apparent first-order terminal elimination half-life
t_{last}	Time to reach the last quantifiable plasma concentration
t_{max}	Time of maximum observed plasma concentration
t_{ss}	Time to achieve pharmacokinetic steady state
15(S)-HEPE EE	15-hydroxy eicosapentaenoic acid ethyl ester

Objectives and Rationale

Overview of Study and Planned Analysis

The objectives of this randomized, double-blind, placebo-controlled, Phase II study are as follows.

Efficacy Objective:

- To compare the efficacy of orally administered DS102 versus placebo, in the treatment of adult patients with severe acute decompensated Alcoholic Hepatitis (AH).

Safety Objective:

- To compare the safety of orally administered DS102 versus placebo, in the treatment of adult patients with severe acute decompensated AH.

Pharmacokinetic Objective:

- To evaluate the pharmacokinetics (PK) of 15(S)-HEPE following orally administered DS102 capsules, in six adult patients with AH in an initial pilot phase of the study, followed by trough level assessment of 15(S)-HEPE in all study participants.

Scope

The 3rd objective listed above is the focus of this data analysis plan. This data analysis project covers data receipt and handling, pharmacokinetic data analysis, data display preparation, and summarization of the plasma free and total 15(S)-HEPE concentrations from the Pilot phase of this study. *Note: Although included in the Mock Displays, data display preparation for the Treatment phase of this study is outside the scope of this analysis plan and will be conducted separately.*

Compliance

This analysis is to be done in compliance with current PKPD Strategies Standard Operating Procedures (SOPs) and all applicable regulations and guidances.

Protocol Summary

Study Design

This is a multicenter, double blind, placebo controlled, 2-arm parallel group comparison Phase 2 study. In an initial pilot phase, six patients will receive open label treatment with DS102 1000 mg orally twice daily (BD) within 30 minutes after a meal for 28 days. After the pilot phase, all patients will either receive 1000 mg DS102 (BD) or placebo (BD), in addition to standard of care therapy, within 30 minutes after a meal for 28 days in the two treatment groups of 60 patients each.

DS102 exhibits a t_{max} of approximately 4 to 8 hours and a short elimination half-life ($t_{1/2}$) of approximately 2 hours. High pharmacokinetic (PK) variability has been observed following both single and multiple dosing, and DS102 did not exhibit a linear correlation between increasing dose and resultant systemic exposure. Co-administration with food increased DS102 bioavailability, although there was no difference in bioavailability between normal and high fat diet fed conditions.

Subject Population

Subjects in this study will be male or female patients, aged 18 years or older, with evident severe acute decompensated alcoholic hepatitis.

Treatment Administration

DS102 will be provided as a capsule containing 500 mg of 15(S)-HEPE EE with 5% w/w of colloidal silicon dioxide as viscosity modifier. In the open label pilot phase, 2000 mg (1000 mg BD) will be orally administered as 2 capsules within 30 minutes after a meal for 28 days. In the double-blind phase of the study either 1000 mg (BD) or placebo (BD) will be orally administered, in addition to standard of care therapy, within 30 minutes after a meal for 28 days. Treatment label will be 1000 mg DS102 BD.

After the completion of the open-label phase of the study the DSMB will evaluate the safety and pharmacokinetic data and might recommend a dose adjustment for the double blind randomised phase of the study. The decision to proceed with the double-blind phase of this study will be determined by the DSMB following review of the data from the pilot phase.

Available information on concomitant standard-of-care treatment or medications used to treat comorbidities during the trial will be assessed for potential impact on observed pharmacokinetic results.

Sampling Design

During the study, 8 visits to the clinic are scheduled after the screening visit (Visit 1): one at the start of the comparative treatment period (Baseline/Visit 2) and six in the comparative treatment period (Visit 3/Day 3, Visit 4/Day 5, Visit 5/Day 7, Visit 6/Day 14, Visit 7/Day 21, Visit 8/Day 28 or Early Termination).

Blood samples for PK analysis will be collected via direct venipuncture as per the Study Flow Chart at Visit 2/Baseline, Visit 3/Day 3, Visit 4/Day 5, Visit 5/Day 7, Visit 6/Day 14, Visit 7/Day 21, and Visit 6/Day 28/Early Termination. Trough plasma samples will be obtained from all patients (pilot and double-blind phases) prior to first daily dose on the indicated days. Additional post-dose serial plasma samples will be obtained from the 6 patients of the Pilot phase for full PK characterization on Days 0 and 7 at 0.5, 1, 2, 3, 4, 6, 7, 8, 10, and 12 (before next dose) hours post-dose. A 1 mL blood sample will be taken at each time point. Following centrifugation, plasma samples will be split in two and a back-up sample will be handled as described in the laboratory manual.

Plasma free and total 15(S)-HEPE concentrations will be determined by Charles River Laboratories (Edinburgh Ltd) using validated liquid chromatography tandem mass spectrometry (LC-MS/MS) methods.

Input Data Handling

Evaluability Criteria

The **Pharmacokinetic (PK) Set** will consist of those patients who have at least one quantifiable post-dose plasma 15(S)-HEPE concentration. Patients will be analysed according to the treatment actually taken. An evaluable profile allows the determination of one or more PK parameters and will be determined at the discretion of the pharmacokineticist. The Pharmacokinetic set will be used for the summaries of all PK data.

Off-time Sample Times

Actual sampling times will be used for all analyses. Nominal time will be used to tabulate plasma 15(S)-HEPE concentrations by time and for all figures.

Out of Range Data

Plasma 15(S)-HEPE concentration-time data will be reviewed to confirm all reported values are valid and are within the lower and upper limits of assay quantitation. Values below or above these limits will be identified as BLQ and ALQ, respectively. BLQ values will be treated either as zero for concentrations prior to the first Cmax or as missing values in all other pharmacokinetic analyses and data presentations. ALQ values will be treated as missing in all analyses and presentations.

Detectable Pre-dose Concentrations

Plasma 15(S)-HEPE concentration data will be reviewed for detectable pre-dose concentrations. Detectable values will be handled according to procedures described in applicable PKPD Strategies SOPs.

Outlying Data

Plasma 15(S)-HEPE concentration data will be reviewed for outlying or unexpected post-dose concentrations. Questionable values will be queried for possible reassay, and may be used or excluded at the discretion of the pharmacokineticist with concurrence from the sponsor.

Missing Data

Plasma 15(S)-HEPE concentration data will be reviewed for missing concentrations. Reasons for missing values will be assessed and followed up accordingly.

For any known hemolyzed plasma samples, consistency of the sample concentration with that subject's concentration-time profile will be assessed. If considered inconsistent by the pharmacokineticist, the affected profile may be analyzed either without the concentration for the sample in question or analyzed with and without, whichever is more appropriate at the discretion of the pharmacokineticist with concurrence from the sponsor.

Clinical Observations

If available, clinical observations pertinent to the pharmacokinetic analysis such as body weight, BMI, emesis or concomitant medications may be assessed for potential impact on the outcome of the analysis.

Input Datafile Creation

Source

Data will be obtained directly from the Sponsor or their designee.

Format

Concentration and associated elapsed time (sampling time minus prior dosing time) results will be received in an Excel-readable file format and will be identified by Study Period, Treatment, Subject, and Nominal Time. Data format has not been prespecified, and will be used as received from the Sponsor or their designee.

Precision

Data precision has not been prespecified, and will be used as received. Precision of reported results will follow applicable PKPD Strategy SOPs.

Units

Time is to be reported in hours and plasma 15(S)-HEPE concentrations are to be reported in ng/mL.

Data Analysis

Planned Pharmacokinetic Assessments

Plasma free and total 15(S)-HEPE concentration-time results will be processed according to standard noncompartmental pharmacokinetic analysis procedures using actual sampling times. The software programs to be used are Phoenix WinNonlin Version 6.4 (Certara Corporation, USA), Microsoft Office Excel 2010, and Microsoft Office Word 2010.

Where feasible, the following non-compartmental PK parameters will be generated:

Parameter	Definition	Units	Precision
%Extrap	Percentage of AUC_{inf} obtained by extrapolation	%	1 dp
AUC_{inf}	Area under the plasma concentration-time curve from time 0 extrapolated to infinite time	ng•hr/mL	1 dp
AUC_t	Area under the plasma concentration-time curve from time 0 to the time of the last quantifiable concentration	ng•hr/mL	1 dp
AUC_{tau}	Area under the plasma concentration-time curve over a dosage interval	ng•hr/mL	1 dp
C_{avg}	Average plasma concentration over a dosage interval	ng/mL	3 dp
C_{last}	Last quantifiable plasma concentration	ng/mL	3 dp
C_{max}	Maximum observed plasma concentration	ng/mL	3 dp
Flucp	Fluctuation at pharmacokinetic steady-state	%	1 dp
K_{el}	Apparent first-order terminal elimination rate constant	1/hr	4 dp
R_{ac}	Accumulation ratio at pharmacokinetic steady-state	%	1 dp
$t_{1/2}$	Apparent first-order terminal elimination half-life	hr	1 dp
t_{last}	Time to reach the last quantifiable plasma concentration	hr	1 dp
t_{max}	Time of maximum observed plasma concentration	hr	1 dp
t_{ss}	Time to achieve pharmacokinetic steady state	hr	1 dp

Planned Statistical Assessments

Descriptive statistics will be used to summarize plasma free and total 15(S)-HEPE concentrations and resultant pharmacokinetic parameters by treatment across study subjects. Summary statistics will include number of non-missing observations, geometric mean, mean, standard deviation, coefficient of variation, minimum, median, and maximum as appropriate.

Analysis Output/Summarization

Data displays for patients from the pilot phase and the double-blind phase of the study will be presented separately. Should the study be discontinued after the pilot phase, the listings described in the sections below will be produced for the pilot phase only.

Summarization

Pharmacokinetic analysis methods, results, and conclusions will be summarized in a separate PK Report, with pertinent information included in the clinical study report. Results for plasma 15(S)-HEPE concentrations and 15(S)-HEPE pharmacokinetic parameters will be summarized and discussed relative to differences between treatments and prior study results. Conclusions related to the study objectives will be presented.

Datasets

Plasma 15(S)-HEPE concentration time data used for input into the PK analysis will be provided as a CDISC-compliant PC dataset. Resultant 15(S)-HEPE PK parameter results will be provided as a CDISC-compliant PP dataset.

Data Displays

Planned data displays are listed as follows.

TABLES

In-Text:

Table A. Descriptive Statistics for Plasma Free 15(S)-HEPE Pharmacokinetic Results for 1000 mg BD DS102 Administered Orally Twice-daily to Patients with Alcoholic Hepatitis (Protocol DS102A-05-AH1 – Pilot Phase).

Table B. Descriptive Statistics for Plasma Total 15(S)-HEPE Pharmacokinetic Results for 1000 mg BD DS102 Administered Orally Twice-daily to Patients with Alcoholic Hepatitis (Protocol DS102A-05-AH1 – Pilot Phase).

End-of-Text:

Table 1. Individual Plasma Free 15(S)-HEPE Concentrations (ng/mL) and Descriptive Statistics for 1000 mg BD DS102 Administered Orally Twice-daily to Patients with Alcoholic Hepatitis (Protocol DS102A-05-AH1 – Pilot Phase, Day 0)

Table 2. Individual Plasma Free 15(S)-HEPE Concentrations (ng/mL) and Descriptive Statistics for 1000 mg BD DS102 Administered Orally Twice-daily to Patients with Alcoholic Hepatitis (Protocol DS102A-05-AH1 – Pilot Phase, Day 7)

Table 3. Individual Plasma Free 15(S)-HEPE Concentrations (ng/mL) and Descriptive Statistics for 1000 mg BD DS102 Administered Orally Twice-daily to Patients with Alcoholic Hepatitis (Protocol DS102A-05-AH1 – Pilot Phase, Troughs)

Table 4. Individual Plasma Total 15(S)-HEPE Concentrations (ng/mL) and Descriptive Statistics for 1000 mg BD DS102 Administered Orally Twice-daily to Patients with Alcoholic Hepatitis (Protocol DS102A-05-AH1 – Pilot Phase, Day 0)

Table 5. Individual Plasma Total 15(S)-HEPE Concentrations (ng/mL) and Descriptive Statistics for 1000 mg BD DS102 Administered Orally Twice-daily to Patients with Alcoholic Hepatitis (Protocol DS102A-05-AH1 – Pilot Phase, Day 7)

Table 6. Individual Plasma Total 15(S)-HEPE Concentrations (ng/mL) and Descriptive Statistics for 1000 mg BD DS102 Administered Orally Twice-daily to Patients with Alcoholic Hepatitis (Protocol DS102A-05-AH1 – Pilot Phase, Troughs)

Table 7. Individual Plasma Free 15(S)-HEPE Pharmacokinetic Parameter Values and Descriptive Statistics for 1000 mg BD DS102 Administered Orally Twice-daily to Patients with Alcoholic Hepatitis (Protocol DS102A-05-AH1 – Pilot Phase)

Table 8. Individual Plasma Free 15(S)-HEPE Pharmacokinetic Parameter Values and Descriptive Statistics for 1000 mg BD DS102 Administered Orally Twice-daily to Patients with Alcoholic Hepatitis (Protocol DS102A-05-AH1 – Pilot Phase)

FIGURES

In-Text:

Figure A. Mean (+/-SD) Day-overlay Plasma Free 15(S)-HEPE Concentrations (ng/mL) versus Time (linear and semilogarithmic scales) for 1000 mg BD DS102 Administered Orally Twice-daily to Patients with Alcoholic Hepatitis (Protocol DS102A-05-AH1 – Pilot Phase, Days 0 and 7).

Figure B. Mean (+/-SD) Day-overlay Plasma Total 15(S)-HEPE Concentrations (ng/mL) versus Time (linear and semilogarithmic scales) for 1000 mg BD DS102 Administered Orally Twice-daily to Patients with Alcoholic Hepatitis (Protocol DS102A-05-AH1 – Pilot Phase, Days 0 and 7).

Figure C. Mean (+/-SD) Plasma Free 15(S)-HEPE Concentrations (ng/mL) versus Time (linear and semilogarithmic scales) for 1000 mg BD DS102 Administered Orally Twice-daily to Patients with Alcoholic Hepatitis (Protocol DS102A-05-AH1 – Pilot Phase, Trough Concentrations).

Figure D. Mean (+/-SD) Plasma Total 15(S)-HEPE Concentrations (ng/mL) versus Time (linear and semilogarithmic scales) for 1000 mg BD DS102 Administered Orally Twice-daily to Patients with Alcoholic Hepatitis (Protocol DS102A-05-AH1 – Pilot Phase, Trough Concentrations).

End-of-Text:

Figure 1. Individual Subject-overlay Plasma Free 15(S)-HEPE Concentrations (ng/mL) versus Time (linear and semilogarithmic scales) for 1000 mg BD DS102 Administered Orally Twice-daily to Patients with Alcoholic Hepatitis (Protocol DS102A-05-AH1 – Pilot Phase, Day 0).

Figure 2. Individual Subject-overlay Plasma Total 15(S)-HEPE Concentrations (ng/mL) versus Time (linear and semilogarithmic scales) for 1000 mg BD DS102 Administered Orally Twice-daily to Patients with Alcoholic Hepatitis (Protocol DS102A-05-AH1 – Pilot Phase, Day 0).

Figure 3. Individual Subject-overlay Plasma Free 15(S)-HEPE Concentrations (ng/mL) versus Time (linear and semilogarithmic scales) for 1000 mg BD DS102 Administered Orally Twice-daily to Patients with Alcoholic Hepatitis (Protocol DS102A-05-AH1 – Pilot Phase, Day 7).

Figure 4. Individual Subject-overlay Plasma Total 15(S)-HEPE Concentrations (ng/mL) versus Time (linear and semilogarithmic scales) for 1000 mg BD DS102 Administered Orally Twice-daily to Patients with Alcoholic Hepatitis (Protocol DS102A-05-AH1 – Pilot Phase, Day 7).

